#### *Statistical analysis*

The IBM SPSS Statistics version 20.0 software package was used for analysis. Categorical variables are expressed as numbers and percentages, whereas continuous variables are summarized as mean and standard deviation and as median and minimum- maximum where appropriate. To compare categorical variables between the groups the chi-square test was used. The Shapiro-Wilk test was used to confirm the normality of distribution for continuous variables. For the comparison of continuous variables between two groups, the Student t test or Mann-Whitney U test was used depending on whether the statistical hypotheses were fulfilled. To evaluate the change in OA measurements obtained in the time interval and to compare the trend in OA measurements between groups, the Repeated Measurements Analysis was applied. The level of  $p<0.05$  was considered as statistically significant.

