## **Study Protocol**

The study was designed as a single-blind, prospective, randomized controlled study with a 2-month follow-up period, carried out in rheumatology outpatient clinic, between March 2017 - January 2019. SSc patients who fulfilled the *American College of Rheumatology* (ACR) 2013 criteria with an OA of <40 mm were included in the study. All patients were previously undergone dental examination by a dentist to exclude oral manifestations and dysfunction of temporomandibular joint that may interfere with attempts to exercise. Patients with missing teeth, dysfunction of temporomandibular joints, oral malignancy, recent dental procedures, multiple active digital ulcers and diagnosed psychiatric conditions were excluded. The study has been approved by the local ethical committee (10.06.2016; protocol number:54) and the written informed consent was taken from all the patients included in the study.

Patients' sociodemographic properties were recorded at the first visit. Disease duration was calculated from the first manifestation of the disease. The severity of the disease was evaluated by Medsger's disease severity scale. Patients were randomly divided into two groups. Randomization was done as the sealed envelope method. After the informed consent was taken, the opaque envelope that the patient have chosen was opened and patients were offered the allocated treatment regimen. Group 1 was given exercise regimen and oral hygiene care advices for the first one month; followed by no exercise but oral hygiene care advices for the next four weeks. Group 2 received oral hygiene care advices for the first one month, followed by the exercise regimen twice a day along with oral hygiene care advices for the next four weeks . Oral care advices were given to every participant by a dentist involved in the study at their first visit. The reason of this design aims to increase the sample size to be analyzed receiving exercise treatment, since scleroderma caused microstomia is a rare condition. The exercise program was demonstrated to patients by a clinician at the first visit and given to all patients printed as a manual to be done every day for one month duration of the exercise program. Additionally, a diary was given to patients to mark when they have completed the exercise and to note in the case of pain on daily basis. The exercise regimen was developed on the basis of previous studies and clinical knowledge.

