Patients' OA was measured at baseline, 1-month, and 2-months by an experienced dentist at the faculty of dentistry. All the measurements were done by the same dentist who is blind to the exercise regimens to provide consistency. The OA was measured using the interincisal distance between the maxillary and mandibular central incisors in the midline. Patients were asked to open their mouth as wide as they could in the natural head position. The linear distance from the incisal edge of the upper central incisor to the incisal edge of the lower central incisor was recorded using a dental bow compass and measured using a millimeter ruler. Each subject was measured three times every two minutes and the highest value of these three measurements was recorded.

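### The OA analysis names no month-1 contrast, the only randomised exercise versus no-exercise comparison, and no baseline adjustment; a month-1 ANCOVA is a cheap improvement

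*Combined protocol and SAP*

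**What the plan says.** The Study Protocol section sets out two sequences. "Group 1 was given exercise regimen and oral hygiene care advices for the first one month; followed by no exercise but oral hygiene care advices" in the second month. "Group 2 received oral hygiene care advices for the first one month, followed by the exercise regimen twice a day". The stated reason for the design is that it "aims to increase the sample size to be analyzed receiving exercise treatment, since scleroderma caused microstomia is a rare condition". Entry is limited to patients "with an OA of <40 mm were included in the study".

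There are three assessments: "OA was measured at baseline, 1-month, and 2-months by an experienced dentist".

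The Statistical analysis section gives OA one method with two purposes. The first purpose is stated as "To evaluate the change in OA measurements obtained in the time interval". For the second, the wording is "to compare the trend in OA measurements between groups, the Repeated Measurements Analysis was applied". No model form, visit, contrast, primary comparison or covariate is stated. The only other test for a continuous variable is general and also unadjusted: "For the comparison of continuous variables between two groups, the Student t test or Mann-Whitney U test was used". It is tied neither to OA nor to month 1.

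The Study Protocol section also describes the exercise programme as shown to patients at their first visit, with the printed manual going to everyone. It does not say whether Group 2 received these at that visit or when its own exercise month began.

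**The concern.** The schedule leaves one clean randomised comparison, at month 1. By month 2 both groups have been assigned a month of exercise, and a between-group difference then reflects order, carry-over and loss of effect. A reader who wants to know whether exercise improves OA more than hygiene advice alone needs the month-1 contrast, and the plan does not commit to it.

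Two things follow. First, a significant group-by-time result would not show by itself that exercise differs from no exercise, and a null trend result could hide a real month-1 effect. Second, baseline OA is collected from every patient but is not stated to be used as a covariate. The plan itself justifies the design by the rarity of the condition, so information that costs nothing extra should be used.

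**Working it through.** **Inputs.** From the document: OA at three visits, the two sequences, a significance level of 0.05 and the entry limit of 40 mm. The document gives no sample size, power, effect or SD, so there is no planned figure to reproduce. Assumed throughout: 1:1 allocation, two-sided testing, n per arm of 10 to 20, baseline to month-1 correlation rho of 0.5 to 0.9, SD ratio k = month-1 SD / baseline SD, and for power an effect of 0.6 baseline SD.

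**Step 1: what each visit compares (scheduled treatment).**

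| Visit | Group 1 so far | Group 2 so far |
|---|---|---|
| Baseline | none | none |
| Month 1 | exercise | no exercise |
| Month 2 | exercise, then none | none, then exercise |

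A group-by-time test over three visits has 2 degrees of freedom and pools the last two rows.

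**Step 2: the linear-trend reading.** With equally spaced visits the weights are -1, 0, +1, so month 1 drops out. Suppose Group 1 gains D by month 1 and keeps it, and Group 2 gains D in month 2. The group difference in trend is D - D = 0, so power equals the significance level, 5%, however large D is.

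**Step 3: ANCOVA against the change score at month 1.** If baseline is the first outcome level, the month-1 component of the interaction is the difference in mean change. With baseline SD = 1:

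- change-score variance = 1 + k² - 2·rho·k
- ANCOVA variance = k²(1 - rho²)
- cost of estimating the slope = factor 1 + 1/(2n - 4): 1.028, 1.038 and 1.063 at 20, 15 and 10 per arm

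Example (rho 0.5, k = 1, n = 20): 0.75/1.00 × 1.028 = 0.771, a net saving of 23%.

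| Net variance ratio | rho 0.5 | 0.7 | 0.8 | 0.9 |
|---|---|---|---|---|
| k = 1, n = 20 | 0.771 | 0.874 | 0.925 | 0.976 |
| k = 1, n = 10 | 0.797 | 0.903 | 0.956 | 1.009 |
| k = 1.1, n = 20 | 0.840 | 0.947 | 0.995 | 1.027 |
| k = 1.1, n = 15 | 0.849 | 0.956 | 1.005 | 1.038 |
| k = 1.1, n = 10 | 0.869 | 0.979 | 1.029 | 1.062 |
| k = 1.2, n = 15 | 0.904 | 1.003 | 1.035 | 1.015 |

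The first formula minus the second is (1 - rho·k)², which is never negative. The loss is therefore bounded by the slope cost alone: 1/36 = 2.8%, 1/26 = 3.8% and 1/16 = 6.3% at 20, 15 and 10 per arm. It is reached when rho·k = 1.

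**Step 4: the entry limit.** Truncating baseline OA narrows its spread and pushes k above 1. Assume a bivariate normal with equal SDs before truncation, and let v be the truncated share of baseline variance. The ratio before the slope cost is (1 + rho)/((1 + rho) + (1 - rho)v). If the limit keeps the lower 80%, v = 0.583, and the net ratios at 20 per arm are 0.861, 0.932, 0.965 and 0.997: savings of 14%, 7%, 3% and 0%. If it keeps the lower 50%, v = 0.363 and the savings are 8%, 3%, 1% and -1%.

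**Step 5: power at 20 per arm, k = 1, D = 0.6.** The 2-df columns are for Group 1 keeping its gain and Group 2 catching up.

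| rho | Month-1 change score | Month-1 ANCOVA | 2-df test | 2-df test, adjusted |
|---|---|---|---|---|
| 0.5 | 46% | 56% | 45% | 49% |
| 0.7 | 67% | 72% | 68% | 69% |
| 0.8 | 83% | 86% | 85% | 86% |
| 0.9 | 98.5% | 98.7% | 99.2% | 99.1% |

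If Group 1 instead loses its gain in month 2 (rho 0.5), the 2-df test has 91.4% power unadjusted and 90.5% adjusted. That is well above the month-1 contrast, but the extra power comes from month 2.

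**The case against.** The strongest reply is that nothing here is wrong: the change score is unbiased under randomisation, and ANCOVA is an efficiency preference whose size rests wholly on assumed inputs. That stands as far as it goes. The one relevant fact in the document, the 40 mm limit, favours k above 1 and so the smaller savings. Losses are not confined to correlations near 0.9: they appear at 0.8 with k = 1.1 and at 0.7 with k = 1.2, both at 15 per arm. For the plan's own 2-df test, adjustment adds little or nothing. None of this answers the unnamed contrast, which is the larger gap.

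Three stronger readings are tempting, and the document does not support them:

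- **Group 2 had not been offered exercise by month 1.** The accounts of the first-visit demonstration and of the manual leave this open. What the text supports is that Group 2 was not yet scheduled to exercise. The passages must be reconciled.
- **The plan's between-group analysis simply is a change-score comparison.** The change score is at most one component of a three-visit analysis.
- **Month-1 OA is to be compared by an unadjusted t test.** Against that test ANCOVA would save 23% to 80% at 20 per arm, since (1 - rho²) × 1.028 runs from 0.771 to 0.195. But the section assigns OA to the repeated-measures analysis.

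**Conclusion.** The concern holds as a cheap improvement. The firm part needs no assumed numbers: month 1 is the only randomised comparison of a group assigned exercise with one not yet scheduled to exercise, and the plan names no contrast there. Under a linear-trend reading that comparison would receive no weight; under the 2-df reading it is mixed with month 2.

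The adjustment part is modest and conditional. At 20 per arm it is worth 2% to 23% of the variance with equal SDs, between a 16% saving and a 3% loss with k = 1.1, and 0% to 14% under the 80% truncation model. The worst cases are a loss of about 6% at 10 per arm with k of 1.1 to 1.2, and about 1% at 10 per arm with k = 1 and rho 0.9. A reader should not infer bias, or that adjustment always helps. Confidence in the size is medium, because rho, k and n are not in the document. The reading of baseline as the first outcome level is likely but not stated.

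**What to change.** Name the month-1 between-group contrast as the analysis of exercise versus no exercise, by allocated group. Estimate it with a 95% CI by ANCOVA of 1-month OA on group and baseline OA, in patients with a month-1 value, and report how many are missing.

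A close but not identical alternative is a mixed model of OA at all three visits, with visit effects, group-by-visit terms at months 1 and 2 only (a common baseline mean) and unstructured covariance. It also keeps patients with a missing visit.

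Keep the existing repeated-measures analysis as supportive, for within-group change and trend, and state its model form and what trend means. Reconcile the first-visit demonstration and distribution of the manual with Group 2's deferred schedule, so that the month-1 comparator is clearly described.

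The cost is wording and one degree of freedom, with no new visits or data; the precision downside is the slope cost shown in the working. The section is written in the past tense, so if the data have already been analysed, label the ANCOVA as an added analysis.
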